Donor human milk for infants with Neonatal Abstinence Syndrome (NAS) [name], DO, MHA, [name], MSPH, Ph.D., [name] Background

Neonatal Abstinence Syndrome (NAS) is a drug withdrawal syndrome that occurs primarily after antenatal exposure to opiates. Symptoms may be present at birth, but often peak at 48-72 after delivery. The onset of symptoms is affected by the half-life of the opiate used during pregnancy in combination with maternal and infant metabolism. The incidence of NAS has increased substantially since 2000 both nationally and in the Commonwealth of Kentucky, leading to a significant increase in healthcare resource utilization and (Figure 1).

The 2012 National Survey on Drug Use and Health found that illicit drug abuse affected ~130,000 pregnancies in the United States from 2011-2012 and that approximately 20% of those pregnancies (26,000) involved opiates. (SAMSA Center for Behavioral Health Statistics and Quality, National Survey on Drug Use and Health, 2009-2012). Patrick et al. utilized the Kids' Inpatient Database (KID) from the Agency for Health Care Research and Quality to evaluate the incidence of maternal opiate use during pregnancy¹. He and his team noted a substantial increase in the number of mothers using opiates - 1.19 per 1000 hospital births in 2000 to 5.63 per 1000 hospital births in 2009. As a result, there was an increased diagnosis of NAS from 1.20 per 1000 hospital births in 2000 to 3.39 per 1000 hospital births in 2009. This is a 2.8-fold increase which means that every hour of every day, 1 neonate in the United States undergoes drug withdrawal.

The Kentucky Injury Prevention and Research Center reported that 824 infants in the state of Kentucky were hospitalized for neonatal withdrawal after exposure to opiates in 2012. This represents an 18% increase from 2011 and a 4.5 fold increase from 2005. (Kentucky Injury Prevention and Research Center. Data for 2010-2012). Neonatal Abstinence Syndrome is an issue of epidemic proportions both for Kentucky and the nation. It results in prolonged hospitalizations and increased healthcare costs. In 2009, the total charges for NAS treatment were noted to be approximately \$720 million nationally, up from approximately \$190 million in 2000¹. Kentucky data from 2012 report a \$40 million dollar cost for neonatal drug withdrawal treatment, which has increased from \$200,000 in 2000. (Kentucky Injury Prevention and Research Center. Data for 2010-2012). The majority of these costs (75-80%) are paid by the state Medicaid program (Figure 2).

Precipitous removal of exogenous opiates at the time of delivery results in unopposed stimulation by cAMP and which increases norepinephrine levels and results in clinical symptoms of drug withdrawal in the neonate². Symptoms include central nervous system (CNS) signs (seizures, irritability, tremors), autonomic disturbances (sweating, yawning, nasal stuffiness, low grade fever, mottling) and gastrointestinal (GI) dysfunction (diarrhea, vomiting, poor feeding, and regurgitation). The cohort of withdrawal symptoms is dictated by the location of μ opioid receptors, which are concentrated in the brain but are also found in sensory nerves, mast cells and in the GI tract³.

Treatment of withdrawal symptoms includes symptomatic care for mild symptoms and pharmacological intervention in addition to symptomatic care for moderate to severe symptoms. The American Academic of Pediatrics and experts in the field recommend opioid replacement therapy as the

first line pharmacologic intervention in opioid-induced withdrawal. The most commonly used medication is oral morphine. Phenobarbital and clonidine have been used as adjuvant therapies with some success in infants with more severe symptoms. Initiation, escalation and weaning of pharmacologic therapy are based on observer rated scales, the most common of which is the Finnegan Scale⁴. Although observer-rated scales are an essential component in the assessment and treatment of neonatal drug withdrawal, they lack rigorous psychometric testing to establish reliability and validity, are subjective and have been difficult to standardize across nurseries⁵.

Infants undergoing opiate withdrawal, as noted above, have feeding difficulty, including spitting, regurgitation and diarrhea. The Finnegan scoring tool includes a series of feeding assessments within the total scoring algorithm (Table 1). Human milk has been shown to be the best tolerated nutritional support for most infants and is cited by the AAP as the preferred method for feeding all infants⁶. However, the AAP considers the use of marijuana, cocaine, methamphetamines and unsupervised opiate use during pregnancy to be a contraindication to breastfeeding⁷. For most street drugs, the risks to the infant of ongoing active use by the mother outweigh the benefits of breastfeeding because the doses of the drug(s) being used and contaminants within the drug are unknown⁸⁻¹¹. The AAP does recognize that if a mother is in a supervised methadone treatment center and is free from using other drugs of abuse then breastfeeding is an essential component of the infant's care. However, most infants with NAS are fed formula for a variety of reasons, including concerns about continued maternal use.

Human milk is a complete nutritional food for the first 6 months of life in the term infant. Aside from its nutritional composition (specific for the support of the human infant), it contains hormones, immunoglobulins and growth factors that stimulate gastrointestinal growth and motility which, in turn, promote the maturation and protection of the GI tract. Mediators such as neurotensin and motilin promote GI motility while free amino acids feed intestinal growth ^{12, 13}. Human milk feeding has been shown to increase gastric empyting ^{14, 15} and lactase activity ¹⁶ in the gut which improves feeding tolerance. A human milk diet is also associated with post-natal intestinal colonization by beneficial bacteria (Lactobacillus and Bifidobacteria). In summary, when compared to formula feeding, human milk appears to be a more suitable diet for the neonate at risk for GI dysfunction.

Two retrospective studies of the effect of breastfeeding on clinical symptoms of NAS have been reported. McQueen et al reviewed 28 mother-infant pairs with maternal methadone exposure and infant symptoms of NAS¹7. Maternal and infant demographics were recorded along with feeding type, Finnegan scores and infant medication utilization during withdrawal. Feeding cohorts were created by quantifying the duration of breastfeeding during hospitalization. Formula fed infants received >75% of all feedings as formula (n=9), breastfed infants received >75% of feedings at the breast (n=8). The rest were considered combination feeders (n=11). Combination feeders were slightly less mature (35.6 weeks) and of lower birth weight (2608 g) than breastfed (38.8 weeks and 3025 g) or formula fed (39.1 weeks and 3302 grams). Breastfed infants received fewer scores, had significantly lower overall Finnegan scores and fewer scores >8 when compared to formula and combination fed infants (p≤0.001).

Dryden et al. performed a retrospective cohort study of 437 infants born to women prescribed methadone in varying doses for their addiction¹⁸. Median gestational age at birth was 38 weeks and birth weight was 2730 grams. Twenty-two percent of infants were breastfed for at least 72 hours. Multivariate logistic regression showed that the prescribed dose of methadone in these women

independently influenced the likelihood of pharmacologic treatment for NAS (p<0.001). However, for infants that were breastfed for at least 72 hours, the odds of needing pharmacologic treatment for NAS was significantly reduced (OR 0.55, 95% CI 0.34 - 0.88, p=0.013).

Maternal opiates are transmitted through the breast milk to the infant. The amount of methadone and buprenorphine transferred in the breast milk has been found to be small, but may be significant enough to lead to some improvement in scores.

While these studies have reported improvements (decreases) in NAS scoring or reduced duration of treatment with breastfeeding, there are no reports that have looked at donor human milk, which is tested to be free of illicit drugs, and its effect on the GI sub-scores of the Finnegan algorithm. Given the general benefits of human milk for the human infant and these limited reports of improved neonatal well-being in breastfed infants with NAS, this study is designed to develop pilot data on the acceptability and benefit of donor human milk for infants undergoing pharmacologic treatment for NAS. Specifically, GI sub-scores, as well as total scores, will be compared between infants historically fed formula and those enrolled in a 2-week donor human milk study period.

Purpose of study: to test the following null hypothesis:

Infants with a diagnosis of neonatal abstinence syndrome (NAS) due to in-utero exposure to opiates, fed donor human milk, will have similar GI/feeding sub-scores of the Finnegan scoring tool when compared to (historic) infants fed formula.

A rejection of the null hypothesis will be used to design a randomized trial of donor human milk in infants with NAS.

Eligibility for study enrollment:

Inclusion criteria:

- Term infants (≥37 completed weeks) with a diagnosis of NAS, due to maternal use of opiates (only)
- Infants will have had moderate to severe NAS symptoms (Finnegan scores >8) that required pharmacologic therapy but have been stabilized (captured) on oral morphine (Finnegan scores less than 8 for 24 hours)
- Breastfeeding is contraindicated or the mother has chosen formula feeding for her baby

Exclusion criteria:

- Preterm infants (<37 completed weeks at birth)
- Infants with intrauterine growth restriction (BW <10th percentile for gestational age) ☐ Mother is providing her own milk

Methods:

Once the infant's withdrawal symptoms have been stabilized with oral morphine and the mother has agreed to participation (signed ICF/RA), infants will be assigned to receive only donor human milk (Co-op donor milk, Medolac Laboratories, Lake Oswego, OR) for a period of 2 weeks. Vitamin supplementation or other nutritional adjustments will be at the discretion of the attending physician.

Infant Finnegan scores will be assessed according to the current NAS protocol. Oral morphine dosing (increases or weaning doses) will be consistent with the current NAS protocol.

Primary outcome:

[figure not shown]
Acceptability (no increase in GI sub-scores compared to historic formula-fed controls) Appropriate growth

See data collection sheet for detailed list of variables.

Statistical analysis:

[figure not shown]
Descriptive statistics will be provided. As this is a pilot study, no inferential statistics will be applied.

Figure 1. Cases of neonatal abstinence syndrome (NAS) in Kentucky (20002012)*

^{*}Data from Kentucky Injury Prevention Research Center, January 2014

Figure 2. Healthcare expenditures (in \$ millions) for treatment of neonatal abstinence syndrome (NAS) in Kentucky (2000-2012)*

2000 2001 2002 2003 2004 2005 2006 2007 2008 2009 2010 2011 2012

Table 1. Modified Finnegan Scoring Tool⁴

System symptoms	Total (frequency)
CNS	
High-pitched cry Continuous high-pitched cry	2 3
Sleeps <1 h after feeding Sleeps <2 h after feeding Sleeps <3 h after feeding	3 2 1
Hyperactive Moro reflex Markedly hyperactive Moro reflex	2 3
Tremors disturbed Mild tremors undisturbed Moderate severe tremors undisturbed	2 3 4
Increased muscle tone	2
Excoriation (specify area)	1
Myoclonic jerks	3
Generalized convulsions	5

^{*}Data from Kentucky Injury Prevention Research Center, January 2014

Metabolic	
Sweating	1
Fever 37.2°C – 38.3°C Fever	1
>38.4°C	2
Frequent yawning >4 x per interval	1
Mottling	1
Vasomotor	
Nasal stuffiness	1
Frequent sneezing >4 x per interval	1
Respiratory	
Nasal flaring	2
Respiratory rate >60/min	1
Respiratory rate >60/min + retractions	2
Gastrointestinal	
Excessive sucking	1
Poor feeding	1
Regurgitation	2
Projective vomiting	3
Loose stools Watery	2
stools	3
GI sub-score range: 0 to 10	
Total score range	0 to 44

REFERENCES

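### GI sub-scores are compared as levels with historic infants and no stated analysis uses the scores charted at capture, so a pre-existing GI difference can look like a milk effect

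*Combined protocol and SAP*

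**What the plan says.** The last paragraph of the Background sets out the comparison: "GI sub-scores, as well as total scores, will be compared between infants historically fed formula and those enrolled in a 2-week donor human milk study". The Primary outcome section makes it the acceptability criterion: "Acceptability (no increase in GI sub-scores compared to historic formula-fed controls". No margin is attached.

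Entry is tied to a scored period before donor milk. Under Inclusion criteria the infant must have had scores above 8 and must be "stabilized (captured) on oral morphine (Finnegan scores less than 8 for 24 hours". Methods places the feed after that: "Once the infant's withdrawal symptoms have been stabilized with oral morphine and the mother has agreed to participation", at which point "infants will be assigned to receive only donor human milk" for two weeks.

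The earlier feed is not named. It was not study donor milk, because that had not begun. Formula is implied by the inclusion criterion "Breastfeeding is contraindicated or the mother has chosen formula feeding for her baby" and by the exclusion "Mother is providing her own milk".

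The Statistical analysis section offers descriptive statistics and no inference. Nothing in the text defines a baseline or a change from baseline. Nor does it give a selection, matching or adjustment rule for the historic infants. A data collection sheet is mentioned for the variable list, but it is not part of the supplied text.

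**The concern.** With historic controls, the level of the GI sub-score on donor milk mixes two things: what the milk did, and how the enrolled infants already differed from the controls when the feed changed. The entry rule seems to equalise the groups, but it acts on the total score and leaves the GI part largely free. The documents also do not say that the historic infants had to meet the same rule.

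The Background itself notes that these scales depend on the observer and are hard to standardise. A stable difference in scoring habit between the two periods would already be visible at capture. In a comparison of levels it would be read as an effect of the feed.

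Because the criterion has no margin, even a small shift can decide it. Enrolled infants who start higher can make an acceptable feed look unacceptable; enrolled infants who start lower can hide a real increase. The result matters beyond the pilot, since the Purpose section links rejection of the null hypothesis to the design of a randomised trial.

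**Working it through.** The plan has no sample size, SD or effect size to reproduce. What can be checked is the scale, what the entry rule allows, and how an imbalance carries through.

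**Inputs.** From Table 1, the GI items are sucking 1, poor feeding 1, regurgitation 2, projectile vomiting 3, and loose stools 2 or watery stools 3; the stated GI range is 0 to 10. From the Inclusion criteria, the total score is below 8 for 24 hours. The documents do not give D, k or b below; they are assumptions.

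**1. GI range.** 1 + 1 + 2 + 3 + 3 = 10, counting the two stool items as alternatives. This agrees with Table 1.

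**2. GI sub-scores allowed at capture.** A total below 8 means at most 7. Every GI value from 0 to 7 can occur: none = 0; poor feeding = 1; regurgitation = 2; vomiting = 3; vomiting + poor feeding = 4; vomiting + regurgitation = 5; vomiting + watery stools = 6; vomiting + regurgitation + loose stools = 7.

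**3. Possible size of the imbalance.** Let D be the donor-milk mean minus the historic mean at capture. If one 2-point item (regurgitation or loose stools) differs in prevalence by 25 to 50 percentage points, D = 2 × 0.25 to 2 × 0.50 = 0.5 to 1.0 points.

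**4. Carry-through with no milk effect.** Let k be the share of D that persists over the two weeks, and b the within-group slope of follow-up on baseline. The apparent effect is then:

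- levels: k × D
- change from baseline: k × D − D = (k − 1) × D
- regression on baseline: (k − b) × D

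| D | k | Levels | Change | Regression, b = 0.5 | Regression, b = 0.7 |
|---|---|---|---|---|---|
| 0.5 | 1.0 | 0.50 | 0.00 | 0.25 | 0.15 |
| 0.5 | 0.7 | 0.35 | −0.15 | 0.10 | 0.00 |
| 0.5 | 0.4 | 0.20 | −0.30 | −0.05 | −0.15 |
| 1.0 | 1.0 | 1.00 | 0.00 | 0.50 | 0.30 |
| 1.0 | 0.7 | 0.70 | −0.30 | 0.20 | 0.00 |
| 1.0 | 0.4 | 0.40 | −0.60 | −0.10 | −0.30 |

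The figures scale with D, and a negative D reverses every sign.

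**5. Reading the table.** Change is less biased than levels only when k is above 0.5. For k between 0 and 1 the two err in opposite directions and so bracket the truth. Regression lies between them. It is closer to zero than levels whenever b is positive and below 2k, which holds in every row, but it is not exact unless b equals k.

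**The case against.** Four objections have weight.

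**The imbalance may fade.** Morphine dosing follows the scores under the NAS protocol, and withdrawal resolves with time. A reader might infer that any starting difference passes in full into the primary comparison. That is true only at k = 1, and the documents give no k. The objection limits the size of the problem; it does not remove it.

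**The plan is silent rather than contrary.** A reader might infer that the capture scores are thrown away. The documents do not say so: the data collection sheet may record them and the descriptive statistics may show them. What can be said is that no stated analysis uses them.

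**Change from baseline is not a full remedy.** It over-corrects when the imbalance fades and is worse than levels below k = 0.5. Nor can it be defended on precision in general. With equal SDs before and after and correlation r, the SD of a change score is √(2(1 − r)) times the unadjusted SD: 1.10, 1.00 and 0.77 at r = 0.4, 0.5 and 0.7. The smaller factors √(1 − r²) = 0.92, 0.87 and 0.71 belong to regression on baseline. A plain before/after comparison in the enrolled infants would be weaker still, because it mixes recovery with a baseline window selected for low scores.

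**This is a descriptive pilot, and the historic controls have no selection rule.** Both statements are correct. The first means that the harm is a biased contrast, not an inflated error rate. The second is a wider gap that baseline adjustment cannot close.

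**Conclusion.** The point stands in a limited form. The primary comparison is of GI sub-score levels between non-randomised groups, and no stated analysis uses scores that the entry rule already requires to be charted. The capture rule does not balance the GI part, so an imbalance of D enters as k × D. That is 0.35 to 1.0 points for D of 0.5 to 1 and k of 0.7 to 1, and 0.2 to 0.4 points for the same D at k = 0.4. These sizes are illustrations, because D and k are assumed; that GI sub-scores of 0 to 7 can pass the capture rule follows directly from Table 1.

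The argument needs only that the infants were not yet on donor milk at capture. A reader might infer that all of them were known to be on formula; that is likely, but it is implied rather than stated.

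This is a worthwhile, inexpensive improvement to a descriptive contrast that is meant to inform a randomised trial. It is not a flaw that invalidates the pilot.

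**What to change.** Add to the Primary outcome and Statistical analysis sections:

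- **Baseline.** In both groups, the mean GI sub-score, and separately the mean total score, over the qualifying 24 hours of capture.
- **Start of follow-up.** In historic infants, the end of that 24-hour window. In enrolled infants donor milk also waits for consent, so report the lag from the end of capture to the first donor feed; the two clocks agree only if it is short.
- **Reporting.** Baseline by group; unadjusted two-week levels by group; and a baseline-adjusted descriptive contrast, either regression on baseline or levels within baseline GI strata. This needs no significance test.
- **Supportive display.** Change from baseline in both groups, with a note that it over-corrects by (k − 1) × D if the imbalance fades.

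The cost for enrolled infants is protocol wording and a few score entries already charted to establish capture, with no extra infants, visits or procedures. The real cost lies in the historic charts: the capture window has to be identified and item-level scores abstracted, and the documents do not say whether both can be recovered. Historic infants without an identifiable window should be counted and reported. Baseline adjustment leaves other differences between the cohorts in place, and the report should say so.

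### Do discretionary nutritional adjustments undermine a study of infants assigned to donor milk only?

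*Combined protocol and SAP*

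**What the plan says.** Under Methods, once symptoms are controlled on oral morphine and the mother has consented, "infants will be assigned to receive only donor human milk" for 2 weeks. The next sentence reads "Vitamin supplementation or other nutritional adjustments will be at the discretion of the attending physician". No type, trigger or limit is given for these adjustments.

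The Primary outcome section lists "Acceptability (no increase in GI sub-scores compared to historic formula-fed controls) Appropriate growth", followed by "See data collection sheet for detailed list of variables". The data collection sheet is not part of the text available for review, and figures under both Primary outcome and Statistical analysis could not be read. The readable analysis text promises descriptive statistics and rules out inferential ones.

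The Background says that scores "will be compared between infants historically fed formula and those enrolled in a 2-week donor human milk study period". The hypothesis under Purpose of study is that infants "fed donor human milk, will have similar GI/feeding sub-scores" to those of historic formula-fed infants, and "A rejection of the null hypothesis will be used to design a randomized trial of donor human milk in infants with NAS".

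**The concern.** The word *only* suggests an exclusive diet, while the following sentence opens the diet to adjustments that go beyond vitamins. If an adjustment is made because an infant is growing or feeding poorly (plausible, although no trigger is stated), that infant may then grow appropriately because of the adjustment and still be counted as a success for donor milk. GI sub-scores taken afterwards reflect the adjusted feed, in either direction. If formula were given, the donor milk group would move towards its comparator.

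Two things would be at stake. One is the growth outcome of the pilot itself. The other is the GI sub-score comparison on which the later randomised trial is meant to rest. With no inferential analysis planned, clear reporting is the main protection against misreading. The protocol also describes, in its Background, a retrospective study that did sort infants by what they were actually fed and kept 11 of 28 (11/28 = 39%) apart as mixed feeders.

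**Working it through.** The plan states no figure on this point: no sample size, growth criterion or adjustment rate is visible. The check is therefore mainly one of text, with illustrations on assumed inputs.

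**Do the two Methods sentences conflict?** The first names the milk. The second concerns vitamins and other adjustments made alongside it. If *only* means that donor milk is the sole milk, both can be followed at once. On that reading a formula feed would be a departure from the assigned milk, though the text does not say so expressly.

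**Do the hypothesis and the comparison describe different infants?** The hypothesis concerns infants fed donor milk and does not say donor milk and nothing else. The Background comparison takes infants enrolled in the donor milk period. An enrolled infant on donor milk plus a supplement satisfies both descriptions, so an adjustment does not by itself separate them.

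**How far could growth on donor milk alone be overstated?** Let p be the share growing appropriately on donor milk alone, a the share of the remainder who are adjusted, and r the share of those who recover within 2 weeks. The reported share is p + (1 − p) × a × r, so the excess is (1 − p) × a × r. All values below are assumed.

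| p | a | r | Excess | Reported |
|---|---|---|---|---|
| 0.90 | 0.5 | 0.5 | 0.10 × 0.25 = 2.5 points | 92.5% |
| 0.70 | 0.5 | 0.5 | 0.30 × 0.25 = 7.5 points | 77.5% |
| 0.90 | 1 | 1 | 0.10 × 1 = 10 points | 100% |
| 0.70 | 1 | 1 | 0.30 × 1 = 30 points | 100% |
| any | 0 | any | 0 points | p |

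The 30-point row needs 30% of infants to grow inadequately, every one of them to be adjusted, and every one to recover within 2 weeks. Enrolment is limited to term infants without growth restriction, and the Background regards human milk as nutritionally sufficient for term infants, so that corner is hard to credit. The range avoids zero only because a and r were set at 50% or more.

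**How far could the GI sub-score move?** The shift in the group mean is s × d, where s is the share of scores taken after an adjustment and d the change in score after it. With d = 1 point in either direction, s = 0.10 gives 0.1 and s = 0.30 gives 0.3 on the 0 to 10 scale of Table 1. A shift of that size matters to a no-increase judgement only if the difference from controls is already close to zero.

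**Does the cited study show that adjusted infants must be kept apart?** It classed an infant as breastfed when more than 75% of feedings were at the breast, so its breastfed group could include infants with nearly a quarter of other feeding. Its mixed feeders averaged 35.6 weeks, whereas this study excludes infants below 37 weeks. The 39% describes mixing of breast and formula in a different population and says nothing about how often donor milk would be adjusted.

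**The case for a change.** The strongest case for a change is that even with the sentences compatible, no visible rule says whether data after an adjustment are kept, flagged or shown separately, and recording an adjustment on a data sheet is not a rule for reporting it. Designers of the randomised trial need to know whether the pilot describes donor milk alone or donor milk with discretionary adjustments, and how often adjustments occurred. A count and a short table would cost little.

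Most of this stands as an observation. The visible text is silent, and a summary of all enrolled infants does describe donor milk plus usual adjustments. It does not show that a stated rule or figure is wrong. The excess calculated above is an error only if the target is donor milk alone, which the plan never claims.

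Some further analyses one might request would add little. Splitting GI sub-scores by adjustment status compares groups formed after enrolment, probably because of poor feeding or growth, so it is confounded by indication. A share with appropriate growth and no adjustment cannot be computed until a growth criterion is stated, which is a separate matter. Historic weights would not bear on adjustments at all.

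**Conclusion.** No change to the plan is called for. This is missing detail in a descriptive pilot. Taken as written, the plan summarises every enrolled infant against historic formula-fed infants, which is a legitimate description of donor milk feeding as it would be given in practice. No test, error rate or stated figure is affected.

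The difference from donor milk alone cannot be sized from the documents and may be zero. The illustrative ranges rest wholly on assumed inputs.

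The conclusion assumes that *only* means the sole milk and that adjustments are recorded, which the unseen data collection sheet may already provide for. An analyst would be expected to summarise all enrolled infants, state how many had a non-vitamin adjustment or a formula feed, and word the growth result accordingly. Frequent formula feeding during the 2 weeks would make the comparison harder to interpret, and that same count would reveal it.

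### The stated purpose is to test and possibly reject a null hypothesis, but the analysis section rules out all inferential statistics, so the test cannot be done as written

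*Combined protocol and SAP*

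**What the plan says.** All the relevant statements are in the combined protocol and SAP.

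- **Purpose of study** opens with "Purpose of study: to test the following null hypothesis". The null is that infants with neonatal abstinence syndrome who are fed donor milk "will have similar GI/feeding sub-scores of the Finnegan scoring tool when compared to (historic) infants fed formula".
- The same section gives the result a use: "A rejection of the null hypothesis will be used to design a randomized trial of donor human milk in infants with NAS".
- The end of **Background** says that "this study is designed to develop pilot data on the acceptability and benefit of donor human milk" and that "GI sub-scores, as well as total scores, will be compared between infants historically fed formula" and the infants enrolled in the donor-milk period. It names no method for the comparison.
- **Primary outcome** lists acceptability, defined as "no increase in GI sub-scores compared to historic formula-fed controls", together with appropriate growth. It gives no margin or threshold.
- **Statistical analysis** promises descriptive statistics and adds: "As this is a pilot study, no inferential statistics will be applied".

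The document states no test, significance level, sidedness, confidence interval, sample size or number of historic controls.

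**The concern.** The purpose relies on an event, rejection of the null, that the analysis section makes impossible. A descriptive pilot is legitimate. A plan that promises a test and a decision based on it, and also excludes the test, is not coherent.

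Three things are at stake. First, the stated purpose cannot be carried out, and no other criterion for moving to a randomized trial is given. Second, the primary outcome is a between-group claim of no increase, and it would be reported without any measure of uncertainty. A reader could not tell from the planned report whether there was no increase or too few infants to see one. Third, the next trial will need a between-infant SD and a plausible range for the difference, and the plan commits to neither.

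The direction also differs. A null of similarity has no direction, whereas the primary outcome looks only for an increase. Rejection could therefore mean benefit or harm, and acceptability could be met without rejection.

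**Working it through.** **Step 1: the statements side by side.** This part needs no arithmetic.

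| Section | What it requires or allows |
|---|---|
| Purpose of study | A null hypothesis is tested |
| Purpose of study | Rejection of that null feeds the design of a randomized trial |
| Primary outcome | GI sub-scores are judged against historic controls, in one direction |
| Statistical analysis | Description only; all inference excluded |

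Rejecting a null requires a test, or a confidence interval used as one. The last row removes both, so the second row can never be met. A figure is missing just before the analysis text, but the sentence that excludes inference is complete and unconditional.

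**Step 2: what a no-increase statement leaves open without an interval.** The document gives no sample size and no SD, so this step is illustration only.

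Inputs:

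- Infant-level SD of the GI sub-score: 1.0, 1.5 or 2.0 points (assumed).
- Group sizes of 8 versus 9: the breastfed and formula-fed groups in the 28-pair retrospective study described in Background, used only as a low-end example.
- Group sizes of 10 versus 20 and 20 versus 40 (assumed).
- Scale: Table 1 states a GI sub-score range of 0 to 10.

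Formula, for the 95% half-width of a difference in means:

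half-width = t(0.975, n1 + n2 − 2) × SD × √(1/n1 + 1/n2)

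| n1 vs n2 | t (df) | √ term | SD 1.0 | SD 1.5 | SD 2.0 |
|---|---|---|---|---|---|
| 8 vs 9 | 2.131 (15) | 0.4859 | 1.04 | 1.55 | 2.07 |
| 10 vs 20 | 2.048 (28) | 0.3873 | 0.79 | 1.19 | 1.59 |
| 20 vs 40 | 2.002 (58) | 0.2739 | 0.55 | 0.82 | 1.10 |

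For example, with 10 versus 20 infants and SD 1.0: 2.048 × 1.0 × 0.3873 = 0.79. An observed difference of exactly zero would then have an upper limit of about 0.8 points, or about 1.6 points if the SD is 2.0.

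**The case against.** The strongest reply is that this is a pilot, that the sponsor chose description, and that a 95% confidence interval is itself inferential, so recommending one reverses that choice. Part of this stands: deleting the null-hypothesis and rejection wording is enough to remove the contradiction, and the interval is a recommendation beyond that. Pilot status does not reconcile the text as it is, because the same document makes rejection the basis for the next trial.

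Other points deserve weight:

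- An SD is an ordinary descriptive statistic and the plan does not exclude it. If group size, mean and SD were reported per infant, a reader could compute the interval. That is fair, but the plan does not commit to reporting them or to the infant as the unit of analysis, although scores are repeated within infants.
- Similarity and no increase may be two questions, benefit and acceptability, since Background names both. That is possible, but the document does not say how they relate. The contradiction holds without this point.
- The assumed SDs have no source in the document. Infants enter only after total scores have been below 8 for 24 hours, and averaging over two weeks could bring the infant-level SD below 1.0. The half-widths would then be smaller. They should not determine how serious the point is.
- A t-interval may perform poorly on a bounded score near its floor with few infants, and the document does not say what historic scores are available. Both are real limits on the proposed analysis.

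**Conclusion.** The concern holds. The test and rejection described in Purpose of study cannot occur under the Statistical analysis section, and nothing else in the document reconciles the two. This conclusion rests on the text alone. The half-widths, from 0.55 to 2.07 points across the scenarios, rest entirely on assumed SDs and on group sizes that are not this trial's; they show only that a bare statement of no increase could leave a noticeable increase open.

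This should be fixed, but it does not prevent the study from running. A descriptive comparison with historic controls remains possible under the current text.

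**What to change.** **Minimum.** Delete the null-hypothesis and rejection wording from Purpose of study. This removes the contradiction and keeps the pilot descriptive, but leaves the no-increase outcome without a measure of uncertainty.

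**Recommended.** Change both sections.

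In Purpose of study, replace the null-hypothesis and rejection wording with:

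> The purpose is to estimate the difference in GI sub-scores between donor-milk infants and historic formula-fed infants. The estimate, its confidence interval and the between-infant SD will be used to design a randomized trial.

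In Statistical analysis, replace the sentence that excludes inference with:

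> Each infant's mean GI sub-score over the 2-week period (for historic infants, over a matching period after stabilization) will be computed. The difference in group means (donor milk minus formula) will be reported with a 95% t-based confidence interval and the SD in each group, the infant being the unit of analysis. It will be read in the direction of the primary outcome: the upper limit is the largest increase compatible with the data. The same will be done for total scores. No hypothesis test will be done.

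**Cost.** New wording in two sections and one simple analysis of scores that the planned comparison already needs. The sponsor must first confirm how many historic infants there are and whether their scores can be matched to the same period, because the document states neither. The interval will probably be wide, the pilot gives up any claim of rejection, and an interval does not remove bias from the use of historic controls.
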